12.2 STANDARD INCLUSION RANGES FOR CLINICAL LABORATORY PARAMETERS

Test	Unit	Low	High
Biochemistry			
NA	mmol/L	130	150
K	mmol/L	3.0	5.5
CCA	mmol/L	0.9 x LLN	1.1 x ULN
Urea	mmol/L	N/A	1.75 x ULN
CREAT	umol/L	N/A	1.0 x ULN
eGFR	mL/min/1.73m ²	60	N/A
GLUC	mmol/L	N/A	1.0 x ULN
BILI	umol/L	N/A	1.25 x ULN
ALP	U/L	N/A	1.5 x ULN
AST	U/L	N/A	1.1 x ULN
ALT	U/L	N/A	1.1 x ULN
GGT	U/L	N/A	1.5 x ULN
HDL	mmol/L	0.9x LLN	N/A
LDL	mmol/L	N/A	2.0 x ULN
Haematology			
HGB	g/L	0.9x LLN	1.1 x ULN
PLAT	×10 ⁹ /L	0.9x LLN	1.1 x ULN
WCC	×10 ⁹ /L	0.9x LLN	1.1 x ULN
NEUT	×10 ⁹ /L	1.0 x LLN	1.1 x ULN
LYM	×10 ⁹ /L	1.0 x LLN	1.1 x ULN
Urinalysis			
PROT	N/A	N/A	Trace
KETONES	N/A	N/A	Trace
GLUC	N/A	N/A	Trace
Red Blood Cells	×10 ⁶ /L	N/A	20 (females)* 10 (males) *A result >20 is acceptable for females currently menstruating.
White Blood Cells	×10 ⁶ /L	N/A	10
Casts	N/A	N/A	Occasional

## 1. ABBREVIATIONS

ADaM	Analysis Data Model
AE	Adverse Event
AESI	Adverse Event of Special Interest
ALP	Alkaline phosphatase
ALT	Alanine Aminotransferase
APR28	Adequate Parasitological Response Rate at Day 28
APTT	Activated partial thromboplastin time
AST	Aspartate Aminotransferase
ATC	Anatomical Therapeutic Chemical
AUC	Area Under the plasma Concentration Time Curve
AUC last	Area under the curve from time 0 to last measurable concentration
AUC inf	Area under the curve from time 0 to infinity
β-HCG	β-Human Chorionic Gonadotropin
BDI	Beck Depression Inventory
BIC	Bayesian Information Criteria
BLQ	Below the Limit of Quantification
BMI	Body Mass Index
CDISC	Clinical Data Interchange Standards Consortium
CI	Confidence Interval
CK	Creatine Kinase
CL/F	Apparent Oral Clearance
C max	Maximum plasma concentration observed
COVID-19	Corona virus disease 2019
CRA	Clinical Research Associate
CRF	Case Report Form
CSR	Clinical Study Report
CTCAE	Common Terminology Criteria for Adverse Events
CV%	Coefficient of Variation
DBP	Diastolic Blood Pressure
DTS	Data Transfer Specification
EC50	Concentration at 50% of Maximum Effect
ECG	Electrocardiography
eCRF	Electronic Case Report Form
EDC	Electronic Data capture
EMAX	Maximum Effect
EOS	End of Study
FAS	Full Analysis Set
FSH	Follicle-Stimulating Hormone
G6PD	Glucose-6-phosphate dehydrogenase
GGT	Gamma Glutamyl Transferase
HBsAg	Hepatitis B Surface Antigen
HEENT	Head, Eyes, Ears, Nose, Throat
HIV	Human Immunodeficiency Virus
HR	Heart Rate
IBSM	Induced Blood Stage Malaria
IIV	Inter Individual Variability
IMP	Investigational Medicinal Product
INR	International Normalized Ratio
LDH	Lactate Dehydrogenase
LLOQ	Lower Limit of Quantification
LOQ	Limit of Quantification
MedDRA	Medical Dictionary for Regulatory Activities
MIC	Minimum Inhibitory Concentration
MMV	Medicines for Malaria Venture
MPC90	Minimal Parasiticidal Concentration
NCA	Non-Compartmental Analysis
ND	Non Detect
NLME	Nonlinear Mixed Effects

PC	Pharmacokinetics Concentration
PD	Pharmacodynamics
Pf iRBC	P.falciparum Infected Red Blood Cell
pfMGET	Male gametocyte-specific transcript
pfSBP-1	Ring-stage transcript
pfs25	Female gametocyte-specific transcript
PK	Pharmacokinetics
PKPD	Pharmacokinetic-pharmacodynamic
PN	Preferred Name
PRR 48	Parasite Reduction Ratio Over 48 hours
PT	Preferred Term
PCt 1/2	Parasite Clearance Half-Life
QIMRB	QIMR Berghofer Medical Research Institute
qPCR	Quantitative Polymerase Chain Reaction
qRT-PCR	Quantitative Reverse Transcriptase Polymerase Chain Reaction
QTcB	Corrected QT interval with Bazett's Formula
QTcF	Corrected QT interval with Fridericia's Formula
RAT	Rapid Antigen Test
SAE	Serious Adverse Event
SAEM	Stochastic Approximation Expectation Maximization
SAP	Statistical Analysis Plan
SAS	Statistical Analysis System
SBP	Systolic Blood Pressure
SBQ	Swiss BioQuant Central
SD	Standard Deviation
SDRT	Safety Data Review Team
SDTM	Study Data Tabulation Model
SE	Standard Error
SOC	System Organ Class
SOP	Standard Operating Procedure
SRC	Safety Review Committee
SSR	Southern Star Research
t 1/2	Elimination Half-Life
TEAE	Treatment Emergent Adverse Event
T max	Time to Reach Maximum Plasma Concentration
VIS	Volunteer Infection Study
Vss/F	Apparent Volume of Distribution at the Steady State After Single Dose
VPC	Visual Predictive Check
Vz/F	Apparent Volume of Distribution after Single Dose
WOCBP	Women of Child Bearing Potential
WHODrug	World Health Organization Drug Dictionary
λ z	Lambda-z: Slope of the apparent elimination phase

## 2. INTRODUCTION

The following Statistical Analysis Plan (SAP) provides the outline for the statistical analysis of the data from the MMV\_MMV367\_22\_01 study. The SAP details the methods for statistical analysis of outcomes relating to safety, pharmacokinetics (PK), pharmacodynamics (PD), and population modelling of pharmacokinetic / pharmacodynamic (PK/PD) data arising from this clinical trial. This SAP has been developed and finalised prior to database lock and final analysis.

Planned analyses identified in this SAP may be included in the clinical study report (CSR), regulatory submissions, and future manuscripts. In addition, post hoc exploratory analyses not necessarily identified in this SAP may be performed to further examine study data. Any post hoc, or unplanned, exploratory analyses performed will be clearly identified as such in the final CSR and in any publications.

Any significant changes from planned analyses will also be described in the final CSR.

### 3. PROJECT OVERVIEW

#### 3.1 Study Design

This is an open-label, adaptive study that will utilise the *P. falciparum* induced blood stage malaria (IBSM) model to characterise the pharmacokinetic/pharmacodynamic (PK/PD) profile and safety of MMV367.

Up to 18 participants will be enrolled in cohorts of up to 6 participants each. The study will proceed as follows for all participants:

- Screening period of up to 28 days to recruit healthy adult participants.
- Day 0: Intravenous inoculation with approximately 2,800 viable *P. falciparum*-infected erythrocytes.
- Days 1-3: Daily follow up via phone call or text message.
- Days 4-7: Daily site visits for clinical evaluation and blood sampling to monitor malaria parasitaemia via quantitative polymerase chain reaction (qPCR).
- Day 7 PM: Start of confinement within the clinical trial unit.
- Day 8: Administration of a single oral dose of the investigational medicinal product (IMP) (MMV367). Different doses of MMV367 will be administered across and within cohorts in order to effectively characterise the PK/PD relationship.
- Days 8-11: Regular clinical evaluation and blood sampling to monitor malaria parasitaemia and measure MMV367 plasma concentration.
- Day 11 AM: End of confinement within clinical trial unit.
- Days 12-23: Outpatient follow-up for clinical evaluation and blood sampling.
- Day 24: Initiation of compulsory definitive antimalarial treatment with Riamet® (artemether/lumefantrine) and/or other registered antimalarials if required. Treatment will be initiated earlier than Day 24 in the event of:
  - Insufficient parasite clearance following IMP dosing (parasitaemia not reduced  $\geq 10$ -fold by Day 10 compared with peak parasitaemia on Day 8).
  - Parasite regrowth following IMP dosing (initial parasite clearance is followed by asexual parasite regrowth above 5000 parasites/mL).
  - Participant discontinuation/withdrawal
  - Investigator's discretion in the interest of participant safety.
- Day 27: End of study visit for final clinical evaluation and to ensure complete clearance of malaria parasitaemia (at least one negative malaria PCR result required).

MMV367 will be administered as a single oral dose on Day 8, with different doses to be tested across and within cohorts to effectively characterise the PK/PD relationship.

Participants will be randomised to a dose group on the day of dosing. The highest dose of MMV367 administered in this study will be no more than 1500 mg.

[figure not shown]
The doses to be tested in Cohort 1 will be as follows:

MMV367 dose	20 mg	90 mg	1500 mg
Number of participants	3	2	1

The Safety Data Review Team (SDRT) will meet following the completion of Cohort 1 to review all safety, PK, and PD data. Doses to be tested in Cohort 2 will be informed by the results obtained in Cohort 1 and will be designed to refine the PK/PD parameter estimates. It may be necessary to test a dose lower than 20 mg in Cohort 2 if PK/PD parameters such as the EC50 were not sufficiently well estimated in Cohort 1. It may also be necessary to obtain additional data at the dose levels tested in Cohort 1. The maximum dose in Cohort 2 will not exceed 1500 mg. Specific doses, and the number of participants per dose, to be tested in Cohort 2 will be decided by the SDRT based on PK/PD simulations.

The SDRT will meet following the completion of Cohort 2 to review all safety, PK, and PD data. If the SDRT deems sufficient data has been obtained to achieve the primary endpoint (i.e., the PK/PD relationship of MMV367 has been appropriately characterized), a third cohort of participants will not be enrolled. If the SDRT deems further data is necessary, doses for Cohort 3 will be selected as described above for Cohort 2.

### 3.2 Schema

### 3.3 Schedule of Activities

The below table summarises the activities and procedures to be conducted as per this protocol during screening, eligibility, malaria inoculation, out patient monitoring, IMP administration and clinic confinement, and at the end of study.

#### Screening and malaria challenge period

Study Day	-28 to -1	-3 to -1	0	1	2	3	4	5	6	7 AM
	Screening	Eligibility confirmation	Pre-inoculation	Post-inoculation	Phone contact		Outpatient visits			
Informed consent	X									
Beck Depression Inventory	X									
Cardiovascular risk	X									
Demography	X									
Medical history	X		X							
Prior medications	X		X							
Eligibility	X	X	X							
Urine drug screen	X		X							
Alcohol breath test	X		X							
Viral screen blood sample	X									
RBC alloantibody blood sample	X									
Coagulation profile blood sample	X									
COVID-19 rapid test			X							
COVID-19 PCR test		X								X
G6PD test blood sample	X									
Serum pregnancy test blood sample	X c	X d								
Urine pregnancy test (WOCBP)			X							
FSH test (post-menopausal women)	X									
Urinalysis sample	X	X								
Adverse events				X	X	X	X	X	X	X
Concomitant medications				X	X	X	X	X	X	X
Safety serum retention			X							
Full physical exam	X a									
Abbreviated physical exam			X							
Symptom directed physical exam							X	X	X	X
Malaria clinical score			X				X	X	X	X
Vital signs	X e		X	X			X	X	X	X
Electrocardiograph (triplicate)	X		X							
Haematology blood sample	X	X								X

Study Day	-28 to -1	-3 to -1	0	1	2	3	4	5	6	7 AM
Biochemistry blood sample	X b	X								X
Diary card				X	X	X	X	X	X	X
Phone contact					X	X	X			
Malaria challenge agent administration				X						
Malaria PCR blood sample			X					X	X	X
Future malaria research blood sample (if participant consented)			X							

FSH: Follicle-stimulating hormone; G6PD: Glucose-6-phosphate dehydrogenase; PCR: Polymerase chain reaction; RBC: Red blood cell; WOCBP: Women of childbearing potential.

aBody height to be recorded at screening only.

bLipids included at Screening for cardiovascular risk factor.

cSerum pregnancy test to be performed for all women at Screening.

dSerum pregnancy test to be performed for WOCBP at the eligibility confirmation visit.

eAt screening, vital signs will be measured after the participant has rested in the supine position for 5 minutes. SBP and DBP will be measured again after the participant has transitioned to a standing position for 3 minutes to assess postural hypotension (see Section 5.2, exclusion criterion 10). At all other time-points vital signs will be measured after the participant has rested in the seated position for at least 5 min.

### IMP administration and clinic confinement period

Study Day	7 PM	8										9			10			11
		Pre-dose	0	1	2	3	4	6	8	12	16	24	30	36	48	54	60	
Hours post-IMP dose																		
Urine drug screen	X																	
Alcohol breath test	X																	
COVID-19 rapid test	X																	
Urine pregnancy test (WOCBP)	X																	
Adverse events		X		X	X	X	X	X	X	X	X	X	X	X	X	X	X	
Concomitant medications		X		X	X	X	X	X	X	X	X	X	X	X	X	X	X	
Abbreviated physical exam		X																
Symptom-directed physical exam			X	X	X	X	X	X	X	X	X	X	X	X	X	X	X	
Malaria clinical score		X						X		X		X	X	X	X	X	X	
Vital signs		X						X		X		X	X	X	X	X	X	
Electrocardiograph		X										X			X		X	
Haematology blood sample		X										X						X
Biochemistry blood sample		X										X						X
Malaria PCR blood sample		X			X		X		X	X	X	X	X	X	X	X	X	
Randomisation		X																
IMP administration			X															

IMP PK blood sample		X		X	X	X	X	X	X	X	X	X		X	X		X	X
Parasite ex vivo viability blood sample		X							X		X	X		X	X			X
Future malaria research blood sample (if participant consented)		X																

IMP: Investigational medicinal product; PK: Pharmacokinetics; PCR: Polymerase chain reaction; WOCBP: Women of childbearing potential.

### Outpatient follow-up period

Study Day	12	13	15	17 d	20 d	22	24 d	27 EOS e
Hours (days) post-IMP dose	96±4 (4)	120±12 (5)	168±24 (7)	216±24 (9)	288±24 (12)	336±24 (14)	384±24 (16)	456±24 (19)
Viral screen blood sample								X
RBC alloantibody blood sample								X
Serum pregnancy test blood sample (WOCBP)								X
Urinalysis sample								X
Adverse events	X	X	X	X	X	X	X	X
Concomitant medications	X	X	X	X	X	X	X	X
Safety serum retention blood sample								X
Full physical exam								X
Symptom directed physical exam	X	X	X	X	X	X	X	
Vital signs	X	X	X	X	X	X	X	X
Malaria clinical score	X	X	X	X	X	X	X	X
Electrocardiograph								X
Haematology blood sample			X			X		X
Biochemistry blood sample			X			X		X
Diary card	X	X	X	X	X	X	X	X
Malaria PCR blood sample	X	X	X	X	X	X	X	X
IMP PK blood sample	X	X	X	X	X			
Definitive antimalarial treatment								X b
Parasite drug resistance blood sample				X a				
Parasite ex vivo growth blood sample	X				X c			
Future malaria research blood sample (if participant consented)	X		X					X

EOS: End of study; IMP: Investigational medicinal product; PK: Pharmacokinetics; PCR: Polymerase chain reaction; RBC: Red blood cell; WOCBP: Women of childbearing potential.

aOne blood sample will be collected for parasite drug resistance assessment only in the event of parasite regrowth. This sample will be collected just prior to initiation of definitive antimalarial treatment.

bDefinitive antimalarial treatment to be initiated on Day 24, or earlier in accordance with the criteria specified in section 4.1 of the protocol.

cOne blood sample will be collected for parasite ex vivo growth only in the event of parasite regrowth. This sample will be collected just prior to initiation of definitive antimalarial treatment.

dVisit not required if participant has previously been administered definitive antimalarial treatment and returned at least one negative malaria PCR result.

eParticipants who withdraw, or are withdrawn or discontinued from the trial, will be asked to attend an early termination visit with assessments equivalent to the Day 27 EOS visit.

### 3.4 Objectives

#### 3.4.1 Primary Objective

- To characterise the PK/PD relationship of MMV367 in healthy participants experimentally infected with blood stage *P. falciparum*.

#### 3.4.2 Secondary Objective(s)

- To evaluate the safety and tolerability of single oral doses of MMV367 in healthy participants experimentally infected with blood stage *P. falciparum*.
- To evaluate the safety and tolerability associated with blood-stage malaria infection in healthy malaria naïve participants.
- To characterise the pharmacokinetics of MMV367 following single oral dose administration in healthy participants experimentally infected with blood stage *P. falciparum*.
- To characterise the parasite clearance kinetics following single doses of MMV367 in healthy participants experimentally infected with blood-stage *P. falciparum*.

#### 3.4.3 Exploratory Objective(s)

- To investigate potential resistance of *P. falciparum* to MMV367 in participants experiencing parasite regrowth after MMV367 administration.
- To characterise the effect of MMV367 on *P. falciparum* parasite viability.

### 3.5 Endpoints

#### 3.5.1 Primary Endpoint (s)

- The PK/PD relationship between MMV367 plasma concentrations and blood stage asexual parasitaemia.

#### 3.5.2 Secondary Endpoint (s)

##### 3.5.2.1 Safety Parameters

- The incidence, severity and relationship to MMV367 of adverse events as determined by self-reported symptoms, clinical laboratory analysis, vital signs, physical examinations and ECG assessments.
- The incidence, severity and relationship to the malaria challenge agent of adverse events as determined by self-reported symptoms, clinical laboratory analysis, vital signs, physical examinations and ECG assessments. Additionally, the severity of the induced malaria infection in each participant graded by the malaria clinical score.

##### 3.5.2.2 PK Parameters

- The pharmacokinetics of MMV367 calculated using non-compartmental methods.

Parameters:

$C_{\max}$ : Maximum plasma concentration observed

$t_{\max}$ : Time to reach maximum plasma concentration

$AUC_{\text{last}}$ : Area under the curve from time 0 to last measurable concentration

$AUC_{\text{inf}}$ : Area under the curve from time 0 to infinity

$t_{1/2}$ : Half-life

CL/F: Apparent Oral Clearance

$V_z/F$ : Apparent volume of distribution  
 $\lambda_z$ : Terminal rate constant

### 3.5.2.3 Parasite Clearance Kinetics

- The parasite clearance kinetics following dosing with MMV367 (parasite reduction ratio over a 48-hour period [PRR48] and corresponding parasite clearance half-life [PCt1/2]).

### 3.5.3 Exploratory Endpoint (s)

- Incidence and level of resistance to MMV367 in parasites determined using *in vitro* methods.
- The effect of MMV367 on parasite viability examined by *ex vivo* cultures.

## 3.6 Sample Size

A maximum sample size of up to 18 participants is expected to be sufficient to achieve the primary endpoint of the study, which is to determine the PK/PD parameters of MMV367. This sample size is not based on formal statistical calculations but rather is based on previous experience of characterising the PK/PD relationship of antimalarials using the IBSM model. The specific number of participants required will be dependent on the emerging results during the study; it is possible that less than 18 participants will be required. The SDRT will review the data after the completion of each cohort and decide when sufficient data has been obtained to complete the primary endpoint. No more than 18 participants will be administered IMP in this study.

## 3.7 Treatment Assignment and Randomisation

All participants will receive an identification number (screening number) as soon as they have signed the informed consent form. Participants who meet the eligibility criteria and are enrolled in the study will be assigned an enrolment number on Day 0 immediately prior to administration of the malaria challenge agent. Participants will be randomised within each cohort to a dose group on Day 8, immediately prior to administration of the IMP. A randomisation schedule will be prepared in advance and take in account potential participant withdrawals prior to scheduled dosing with IMP. The details of the randomisation procedure will be described in the randomisation plan. This is an open label study and therefore no blinding will be performed.

### *Replacement of Withdrawn/Discontinued Participants*

Participants who withdraw, or are withdrawn or discontinued from the trial, may be replaced after mutual agreement between the Sponsor and the Principal Investigator. The decision regarding the replacement of participants will be documented.

All withdrawn participants must successfully complete the full course of definitive antimalarial treatment.

#### 4. STATISTICAL CONSIDERATIONS

Data analysis will be performed according to the Sponsor's representative Standard Operating Procedures (SOPs).

The general analytical approach for all endpoints will be descriptive in nature. All summaries will present the data by dose group as well as by all participants combined.

Unless otherwise stated, the following statistical approaches will be taken:

Continuous variables:	Descriptive statistics will include the number of non-missing values, mean, standard deviation (SD), CV%, median, interquartile range, minimum, and maximum. The minimum and maximum values will be presented to the same number of decimal places as recorded in the raw data; mean and median will be presented to 1 decimal place more than raw data; and SD will be presented to two more decimal places than the raw data. The number of decimals for lab parameters may be reduced if the full presentation of the data includes more than 4 significant figures.
Categorical variables:	Descriptive statistics will include frequency counts and percentages per category. Percentages will be rounded to one decimal place, with the denominator being the number of patients in the relevant population.
Imputation:	No imputation will be performed for missing data.
Confidence intervals (CIs):	CIs will be two-sided and will use 95% confidence levels.
Unscheduled Visits	Unscheduled visits that do not have laboratory data on the same visit date will be excluded from summary tables.
Early termination visit	Assessments conducted at Early Termination will be excluded from visit-based summary tables unless otherwise indicated.

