9.4 STATISTICAL ANALYSES

9.4.1 GENERAL APPROACH

Continuous variables will be summarised with the number of observations (non-missing values), mean, standard deviation (SD), median, quartiles, minimum and maximum. The minimum and maximum values will be presented to the same number of decimal places as recorded in the raw data. The mean, median and SD will be presented to one more decimal place than the raw data. Categorical variables will be summarised with the number of observations and the numbers and percent from each category. Percentages will be rounded to one decimal place, with the denominator being the number of participants in the relevant population with non-missing data. No missing data will be imputed. If required, confidence intervals (CIs) will be two sided and will use 95% confidence levels. Any analyses requiring significance testing will use a two-sided test at the 5% significance level.

The inoculation baseline will be defined as the last available assessment prior to administration of the malaria challenge agent. The IMP baseline will be defined as the last available assessment prior to the administration of the IMP. Unscheduled visits will be excluded from summary tables. Assessments conducted at Early Termination will be excluded from summary tables.

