12.1.6 OUTPATIENT MONITORING POST-IMP ADMINISTRATION (DAYS 12 TO 27)

Follow up visits will be undertaken on an out-patient basis for clinical evaluation and blood sampling on the scheduled days described below. Follow up visits may occur more frequently if clinically indicated. Follow up visits on Days 17, 20 and 24 are not required if participant has previously been administered definitive antimalarial treatment and returned at least one negative malaria PCR result.

The following procedures will take place on Day 12±4hrs:

- Obtain malaria clinical score.
- Record vital signs.
- Record AEs and use of concomitant medications.
- Check participant diary cards.
- Perform symptom-directed physical examination if clinically indicated.
- Collect blood samples for:
 - malaria PCR,
 - IMP PK,
 - parasite *ex vivo* viability,
 - future malaria research sample (if participant consented).

The following procedures will take place on Day 13±12hrs:

- Obtain malaria clinical score.
- Record vital signs.
- Record AEs and use of concomitant medications.
- Check participant diary cards.
- Perform symptom-directed physical examination if clinically indicated.
- Collect blood samples for:
 - malaria PCR,
 - IMP PK.

The following procedures will take place on Day 15±24hrs:

- Obtain malaria clinical score.
- Record vital signs.
- Record AEs and use of concomitant medications.
- Check participant diary cards.
- Perform symptom-directed physical examination if clinically indicated.
- Collect blood samples for:
 - haematology and biochemistry,
 - malaria PCR,

- IMP PK,
- future malaria research sample (if participant consented).

The following procedures will take place on Day 17±24hrs:

- Obtain malaria clinical score.
- Record vital signs.
- Record AEs and use of concomitant medications.
- Check participant diary cards.
- Perform symptom-directed physical examination if clinically indicated.
- Collect blood samples for:
 - malaria PCR,
 - IMP PK.

The following procedures will take place on Day 20±24hrs:

- Obtain malaria clinical score.
- Record vital signs.
- Record AEs and use of concomitant medications.
- Check participant diary cards.
- Perform symptom-directed physical examination if clinically indicated.
- Collect blood samples for:
 - malaria PCR,
 - IMP PK.

The following procedures will take place on Day 22±24hrs:

- Obtain malaria clinical score.
- Record vital signs.
- Record AEs and use of concomitant medications.
- Check participant diary cards.

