#### **11.3.8. Malaria Clinical Score**

Malaria clinical score data will be listed for all participants, including the individual scores for each of the 14 signs/symptoms as well as the total score.

The number (and percentage) of participants scoring each symptom (0=absent; 1=mild; 2=moderate; 3=severe) will be tabulated per dose group and per protocol defined timepoint.

The highest score as well as the time(s) to the highest score observed will be tabulated.

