Inoculum Emergent Serious Adverse Events by MedDRA System Organ Class and Preferred Term (All Causalities)	FAS
Treatment Emergent Serious Adverse Events by MedDRA System Organ Class and Preferred Term (All Causalities)	IMP
Overall Summary of Inoculum Emergent Adverse Events of Special Interest (AESI)	FAS
Overall Summary of Treatment Emergent Adverse Events of Special Interest (AESI)	IMP
Inoculum Emergent Adverse Events of Special Interest (AESI) by MedDRA System Organ Class and Preferred Term (All Causalities)	FAS
Treatment Emergent Adverse Events of Special Interest (AESI) by MedDRA System Organ Class and Preferred Term (All Causalities)	IMP
Inoculum Emergent Adverse Events Leading to Study Discontinuation by MedDRA System Organ Class and Preferred Term (All Causalities)	FAS
Treatment Emergent Adverse Events Leading to Study Discontinuation by MedDRA System Organ Class and Preferred Term (All Causalities)	IMP
Summary of Concomitant Medications (FAS)	FAS
Summary of Concomitant Medications (IMP)	IMP
Haematology (Summary and Change from IMP Baseline)	FAS
Haematology (Categorical)	FAS
Biochemistry (Summary and Change from IMP Baseline)	FAS
Biochemistry (Categorical)	FAS
Urinalysis (Continuous) Results and Change from Baseline	FAS
Urinalysis (Categorical) Results	FAS

Vital Signs Results and Change from IMP Baseline	FAS
Abnormal Vital Signs Results	FAS
ECG Results and Change from IMP Baseline	FAS
ECG QTc Categorical Analyses	FAS
ECG Clinical Assessment	FAS
Malaria Clinical Score Summary by Question	FAS
Summary Peak Total Malaria Clinical Score and Time to Peak Total Malaria Clinical Score	FAS

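### The SAP drops the protocol's non-missing-data denominator without declaring it, so by-visit symptom percentages at Days 17, 20 and 24 mix unassessed participants with graded results

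*SAP*

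**What the plan says.** SAP section 4 gives a general rule for categorical variables, to apply unless another is stated: "Percentages will be rounded to one decimal place, with the denominator being the number of patients in the relevant population". Protocol 9.4.1 gives the same rule with one further restriction: "with the denominator being the number of participants in the relevant population with non-missing data". SAP section 13 reports no change to the planned analysis.

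On missing values SAP section 4 says: "No imputation will be performed for missing data". A skipped assessment therefore stays missing.

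SAP 11.3.8 plans a table of the number and percentage of "participants scoring each symptom (0=absent; 1=mild; 2=moderate; 3=severe) will be tabulated per dose group and per protocol defined timepoint". It names no denominator of its own, so the general rule governs. SAP Table B lists this table as "Malaria Clinical Score Summary by Question" and assigns it to the FAS, which SAP 5.1.1 defines as everyone who received the challenge agent.

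The outpatient schedule in both documents includes the malaria clinical score and vital signs on Days 17, 20 and 24, and attaches this footnote to those three days: "Visit not required if participant has previously been administered definitive antimalarial treatment and returned at least one negative malaria PCR result". Protocol 12.1.6 repeats the waiver.

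**The concern.** Two approved documents give programmers different denominators for the same percentages, and nothing says which prevails. Most tables would show no difference if attendance were complete, but here some absence is part of the design. Participants who regrow parasites are treated early and, once PCR-negative, need not attend three of the late visits. Under the SAP rule they stay in the denominator while contributing to no grade.

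The table then shows a percentage that is neither the proportion of those assessed nor a proportion of a fully observed group. Groups are very small (3, 2 and 1 in Cohort 1), so one absence changes the figure a great deal. Absence may also differ between the dose groups shown side by side. Protocol 4.3 predicts regrowth at 20 mg and considers it very unlikely at 1500 mg. The malaria clinical score belongs to a named secondary endpoint, so the table is likely to be read.

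**Working it through.** The documents state no figure on this point, so there is nothing to reproduce. The check compares the two written rules.

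**Notation.** N is the number in the group, m the number not assessed at the visit, and x the number assessed who have a given symptom grade.

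- SAP rule: x / N
- Protocol rule: x / (N − m)
- Total of the four grades (0 to 3) under the SAP rule: (N − m) / N
- Total of the four grades under the protocol rule: 100%

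**Inputs from the documents.** N = 3 for 20 mg in Cohort 1 (protocol 4.3) and at most 18 overall (protocol 9.2). The values of m and x are assumptions, because the documents give neither.

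| N | x | m | SAP rule | Protocol rule | Sum of grades, SAP rule |
|---|---|---|---|---|---|
| 3 | 1 | 0 | 33.3% | 33.3% | 100% |
| 3 | 1 | 1 | 33.3% | 50.0% | 66.7% |
| 3 | 1 | 2 | 33.3% | 100.0% | 33.3% |
| 18 | 2 | 6 | 11.1% | 16.7% | 66.7% |
| 18 | 2 | 9 | 11.1% | 22.2% | 50.0% |

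With m = 0 the rules agree. Otherwise every grade, including grade 0, shrinks by the factor (N − m)/N.

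**Is m > 0 plausible at Days 17, 20 and 24?** Dosing is on Day 8. Protocol 4.3 predicts return to baseline parasitaemia after 20 mg at a median of 7 days, which is Day 8 + 7 = Day 15. The stated 95% interval of 2.5 to 14 days corresponds to Day 10.5 to Day 22. Baseline is expected to exceed 5,000 parasites/mL (protocol 4.2), and regrowth above 5000 triggers early treatment (protocol 4.1). Some 20 mg participants may therefore be treated before the three waivable visits. Treatment alone does not release them, because a negative PCR is also needed. Nor does the waiver mean that they will stay away.

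**A second route, in the overall column.** SAP section 4 also requires summaries for all participants combined. Participants not dosed with IMP on Day 8 are treated and withdrawn (protocol 7.1 and 7.2) but remain in the FAS. Under the literal SAP rule they count in the overall denominator at every later visit, where they have no data.

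**How each rule relates to the whole group.** Take N = 3, m = 2, x = 1. If both absentees are symptom-free, the group figure is 1/3 = 33.3%, which matches the SAP rule, and the protocol rule's 100% is too high. If both have the symptom at the same grade, the group figure is 3/3 = 100%, which matches the protocol rule, and the SAP rule's 33.3% is too low. The documents do not say which case is nearer.

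**The case against.** The strongest reply is that this is a small wording difference in a descriptive study without a hypothesis, and that several apparent consequences do not follow. Most of that stands.

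- **Symptoms understated, most at low doses.** A reader might infer this. The documents do not support it, because those excused are treated and PCR-negative and may have no symptoms. The SAP figure could then equal the group figure, while the protocol figure would describe a selected few.
- **Absence counted as symptom-free.** A reader might infer this too. SAP 11.3.8 has a separate grade 0 and nothing is imputed, so an absentee enters no grade. The counts printed beside the percentages also let a careful reader see the shortfall.
- **Every categorical table affected.** The waiver covers three visits only. The malaria score on Days 12, 13, 15, 22 and 27 is not waivable. Scheduled outpatient haematology and biochemistry fall on Days 15, 22 and 27, and the outpatient ECG and urinalysis on Day 27.
- **The secondary endpoint compromised.** It concerns severity in each participant. The SAP also serves it with individual listings, the highest score and the time to it, none of which uses a by-visit denominator. Protocol 9.4.4 asks only for listings of the score; the percentage table is an SAP addition.
- **Early-termination exclusion.** Both documents leave these assessments out of visit summaries, so this is not a discrepancy.

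The reply does not remove the contradiction. The SAP states a rule that, followed literally, yields grade distributions that do not total 100% at visits where absence is expected. It differs from the protocol without saying so.

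**Conclusion.** The inconsistency is real and undeclared, and its reach is narrow. It affects the malaria clinical score percentages, and any by-visit vital-sign categories, at Days 17, 20 and 24. It also affects the overall FAS column at later visits if anyone is withdrawn before IMP dosing. There the grades total (N − m)/N, so unassessed participants are mixed with graded results. In a group of 3 the two rules can differ by as much as 33.3% against 100.0%, but only under an assumed m of 2; with full attendance they do not differ.

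No direction or size of bias against the whole dose group can be claimed, since both depend on the unknown symptoms and number of absentees. Adverse event incidence, peak malaria score and time to peak, and the primary PK/PD analysis are not affected. It should be corrected before the tables are programmed, as a reconciliation of the two documents and not as a threat to the trial's conclusions.

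**What to change.** In SAP section 4, make the denominator for by-visit categorical summaries the number of participants in the relevant population with non-missing data at that time point, as in the protocol. At each visit, show the number assessed over the number in the group (n/N). State that adverse event incidence keeps the whole analysis set named for each table: the FAS for inoculum-emergent events and the IMP Set for treatment-emergent events. If the SAP rule was intended, section 13 should declare and justify it, and the table should carry a row for participants not assessed.

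The cost is one sentence in the SAP and an n/N entry in the affected table shells, with no change to data collection. The small downside is that the non-missing percentage describes only those who attended, who may differ from those excused. That is why n/N must be shown.
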